5.3 Drop out standard

Subjects who sign the informed consent and do not complete the prescribed observation period regardless of when and where to exit, are called drop out.

- (1) Patients found in the study course who do not meet the inclusion criteria or do follow the exclusion standards.
- (2) Patients who get other irrelevant diseases that could affect the assessment on the efficiency and safety of the drug during the test.
- (3) Patients who receive any drug that influences the assessment on the drug.
- (4) Patients who do not strictly take standard medication because of any reason (e.g. severe side effects).

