2.2 Per-protocol (PP) analysis population

All individuals who violated the study protocol, such as patients not taking at least 80% of treatment drugs, or with unknown post-treatment H. pylori status will be excluded from the PP analysis.

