5.2 Compliance rate

Compliance was defined as either poor when they had taken less than 80% of the total medication or good when they had taken more than 80% medication. Compliance rate is defined as the number of patients with good compliance divided by the total number of population for analysis. These data are presented with number, percentage.

Comparisons of presence of each adverse event and any adverse event between the tailored therapy and empiric therapy will be performed in the ITT analysis populations using the Pearson’s χ^2 , corrected χ^2 or Fisher’s exact test.

5.3 Other Pre-specified Outcome Measures:

(1) Medical cost per patient of tailored or empiric therapy

Medical cost of one patient is overall cost including visit, endoscopy, H. pylori culture, susceptibility testing, eradication treatment, and adverse event treatment.

Comparisons of medical cost between the tailored therapy and empiric therapy will be performed in the PP analysis populations using Student t test.

(2) Ratio of medical cost to H. pylori eradication rate of each therapy

Ratio of medical cost to H. pylori eradication rate of each therapy is defined as average medical cost of the therapy divided by H. pylori eradication rate of one therapy.

(3) Ratio of incremental medical cost to incremental H. pylori eradication rate of tailored compared with empiric therapy

If one therapy cost less and achieved higher eradication rate than the other one, it will be referred to as dominant strategy. If one therapy yielded higher eradication rate but also cost more, an incremental cost-effectiveness ratio (ICER) will be calculated. Obviously, the tailored therapy will cost more because of additional bacterial culture and antibiotic susceptibility testing. So, if eradication rate of the tailored therapy was higher, the ICER of the tailored therapy will be calculated as the ratio of incremental medical cost to incremental H. pylori eradication rate of tailored compared with empiric therapy (in terms of RMB per incremental eradication percentage). If eradication rate of the tailored therapy was equal to or lower than the empiric therapy, the tailored therapy will not be more cost-effective option and the economic evaluation will not be conducted.

6. Additional analyses

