6.4 Effect of compliance on eradication rate

Comparisons of eradication rate of one therapy between good and poor compliance will be performed in the ITT analysis populations who had UBT results using the Pearson's χ^2 , corrected χ^2 or Fisher's exact test.

7. Table Design

Table 1. Baseline characteristics

Variables	Tailored therapy	Empiric therapy	p value
Age, years (range)			
Gender (male/female)			
Diagnosis (Dyspepsia/PUD)			
Antibiotic resistance pattern			
Clarithromycin, n (%)			
Metronidazole, n (%)			
Levofloxacin, n (%)			
All-susceptible, n (%)			
Triple-resistant, n (%)			
Poor adherence*			
Loss of follow-up			

Final SAP

NUD, non-ulcer dyspepsia; PUD, healed peptic ulcer disease.

* Poor adherence, took less than 80% of drugs

Table 2. Eradication rate of each group in ITT and PP analysis

Analysis	Tailored therapy	Empiric therapy	Difference	p value for inequality*	p value for superiority **
ITT (% , n/N)					
95% CI					
PP (% , n/N)					
95% CI					

CI= confidence interval; ITT = intention-to-treat; PP = per-protocol.

* The *p* values were for testing the difference between tailored therapy group and empiric therapy group.

** The *p* values were for testing the superiority of tailored therapy group to empiric therapy group.

Table 3. antibiotic resistance pattern of ITT population

antibiotic resistance pattern (CLA-MET-LEV)	ITT population	Tailored therapy	Empiric therapy
All susceptible			
S-S-S			
Single resistant			
R-S-S			
S-R-S			
S-S-R			
Dual resistant			
R-R-S			
R-S-R			
S-R-R			
Triple resistant			
R-R-R			

CLA, clarithromycin; LEV, levofloxacin; MET, metronidazole; R, resistant; S, susceptible.

Table 4. Eradication rates of tailored and empiric therapy in the presence of antibiotic resistance in the per-protocol population

PP population	Tailored therapy	Empiric therapy	p value
Clarithromycin resistance			
Susceptible			
Resistant			
Metronidazole resistance			
Susceptible			
Resistant			
Levofloxacin resistance			
Susceptible			
Resistant			
Resistance pattern (Clarithromycin-Metronidazole-Levofloxacin)			
S-X-X			
R-S-X			
R-R-S			
R-R-R			

R=resistant; S=susceptible; X=resistant or susceptible.

Table 5. Adverse events and adherence in the treatment groups

Variables	Tailored therapy	Empiric therapy	p value*
Total, n/N (%)			
AE grade			
None/Mild/Moderate/Severe			
AE variety			
Taste alteration			
Dyspepsia			
.....			
.....			
.....			

Skin rash

Discontinued drugs

because of AEs

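### Final SAP 5.3 compares cost only in per-protocol patients, leaves open which eradication rate enters the cost ratio, the ICER and the stop rule, and cancels the ICER item on an assumed cost direction.

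*Combined protocol and SAP*

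**What the plan says.** All references are to the Final Protocol and Final SAP.

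- **Cost comparison, SAP 5.3(1):** "Comparisons of medical cost between the tailored therapy and empiric therapy will be performed in the PP analysis populations using Student t test". Cost per patient covers visits, endoscopy, culture, susceptibility testing, eradication treatment and treatment of adverse events.
- **PP set, SAP 2.2:** protocol violators such as "patients not taking at least 80% of treatment drugs, or with unknown post-treatment H. pylori status will be excluded from the PP analysis".
- **Cost ratio, SAP 5.3(2):** it "is defined as average medical cost of the therapy divided by H. pylori eradication rate of one therapy". No population is named for the eradication rate.
- **ICER, SAP 5.3(3):** "If one therapy cost less and achieved higher eradication rate than the other one, it will be referred to as dominant strategy". The text continues: "Obviously, the tailored therapy will cost more because of additional bacterial culture and antibiotic susceptibility testing". The ICER is calculated if the tailored rate is higher. If it is equal or lower, "the tailored therapy will not be more cost-effective option and the economic evaluation will not be conducted". No population, interval or test enters this condition.
- **Eradication rate, SAP 4.1 to 4.3:** the denominator is whichever population is being analysed, and the rate is tested in both ITT and PP.
- **Objective, Protocol 2.2(3):** cost-effectiveness is a secondary objective, with no condition attached. Protocol 9.3 lists cost, cost ratio and incremental ratio, also without condition.
- **Schedule table:** medical cost is collected at the 4th visit (day 56). Culture and susceptibility testing is done at the 1st visit, before allocation.

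**The concern.** There are two problems.

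First, the cost comparison rests on a subset formed after randomisation, in an open-label trial whose arms receive different regimens. Protocol 5.3(4) lists among drop-outs "Patients who do not strictly take standard medication because of any reason (e.g. severe side effects"). Adverse-event treatment is a listed cost, so the PP restriction can remove patients whose costs the definition is meant to capture. The eradication rate that enters items (2) and (3) is left open and could be chosen after the results are known.

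Second, the stop rule replaces an estimate with a premise. Dominance is defined for either therapy, yet the evaluation stops exactly where empirical therapy could be dominant. It also stops where tailored therapy turned out less effective but cheaper.

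What is at stake is the joint cost-effectiveness conclusion, which serves a stated secondary objective.

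**Working it through.** **1. Does any other section supply the missing population?** No. SAP 4.1 uses a generic denominator, and SAP 4.2 and 4.3 use both ITT and PP. PP is the only population that 5.3 names for cost, so it is the natural source of the average cost in (2) and the cost increment in (3). The gap that remains is the eradication rate.

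**2. Can poor compliers have usable data?** SAP 6.4 compares eradication "between good and poor compliance will be performed in the ITT analysis populations who had UBT results". That analysis presupposes poor compliers who returned for the breath test. The test and the cost record share the 4th visit, so their cost can be recorded too. The documents do not say how many such patients to expect.

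**3. Inputs for the trigger calculation.** Planned rates are 96.5% and 88.9% (SAP section 1). The plan requires 260 + 87 = 347 and allows for 10% loss. Its own figure reproduces: 260 × 1.1 = 286 and 87 × 1.1 = 95.7, rounded up to 96, total 382.

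Assumptions that are not in the documents: loss is independent of outcome and 10% in each arm, and PP equals the patients not lost. The under-80% exclusion is therefore not modelled.

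**4. How often does the rule fire?** The quantity is P(observed tailored rate ≤ observed empirical rate).

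- ITT, loss scored as failure: success probabilities are 0.9 × 0.965 = 0.8685 and 0.9 × 0.889 = 0.8001. Exact binomial enumeration with n = 286 and 96 gives 0.0654.
- Hand check: SE = √(0.8685 × 0.1315/286 + 0.8001 × 0.1999/96) = 0.0454; z = 0.0684/0.0454 ≈ 1.51; upper tail about 0.066.
- PP, and the joint behaviour of the two sets, by simulation of 4,000,000 trials:

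| True rates (tailored v empirical) | Fires on ITT | Fires on PP | ITT and PP disagree |
|---|---|---|---|
| 96.5% v 88.9% (planned) | 6.5% | 1.1% | 6.3% |
| 92.7% v 88.9% (half the planned difference; assumption) | 23.6% | 15.6% | 18.0% |
| 92% v 92% (assumption) | 51.2% | 51.4% | 26.1% |

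About 50% at equal true rates is what any point-estimate rule gives. The informative column is the last one.

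**5. ICER denominator.** At the planned rates the effect is 96.5 − 88.9 = 7.6 points in evaluable patients and 0.9 × 7.6 = 6.84 points on ITT. For the same incremental cost, the ICER on ITT is 7.6/6.84 = 1.11 times as large. Equal incremental cost is itself an assumption, since cost may also differ between the two sets.

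**6. What is lost when the rule fires?** The cancellation sentence stands inside item (3), so the natural reading is that it cancels that item only. The eradication difference with its 95% CI remains (SAP 4.3 and Table 2), as do the cost comparison in (1) and the ratios in (2). The ICER item is lost, and with it any statement that empirical therapy is dominant or that tailored therapy is cheaper.

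**The case against.** The strongest defence is that the SAP does answer the objective when the rule fires: it says that tailored therapy is not the more cost-effective option. If tailored therapy costs more and eradicates no more, that is right. An ICER is undefined at equality and of little use for a dominated option. This stands as a reason not to print a ratio. It does not justify taking the direction of cost as given when cost is being collected.

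Two further points stand. The calculation omits the under-80% exclusion, so it does not measure the effect of restricting cost to PP. And Protocol 5.3 places poor compliers among those who do not complete observation, so many may have no day-56 cost record; SAP 6.4 shows only that some are expected to return.

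A reader might infer more than the documents support:

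- That all economic and effect results vanish when the rule fires. On the natural reading they do not (step 6).
- That the PP restriction favours one therapy. Neither the direction nor the size of any bias in cost can be determined from the documents.
- That culture and testing will be charged to the tailored arm only. SAP 5.3(3) calls them additional to tailored therapy, but the cost definition does not say how they are charged, and every patient undergoes them.

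**Conclusion.** The point holds in limited form. The cost comparison is restricted to a set selected after randomisation. The eradication rate behind the cost ratio, the ICER and the stop condition is not identified. The stop condition relies on an untested cost direction and sits badly with the SAP's own two-way definition of dominance and with an unconditional objective.

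At the planned rates, under the stated loss assumptions, the choice between ITT and PP changes the decision to proceed in 6.3% of trials; the share rises if the true difference is smaller. These figures describe dependence on an unstated choice, not harm.

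Priority is low. These are other pre-specified outcomes and the primary superiority test is untouched. It is worth changing because the change is cheap.

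**What to change.** In SAP 5.3:

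- **(a) One population for cost and effect in items (1) to (3).** Use all randomised patients, with no breath test scored as failure (as in SAP 2.1) and missing cost handled by a stated method such as multiple imputation. Give two sensitivity analyses, each taking cost and effect from the same patients: ITT patients with breath-test results (the set SAP 6.4 uses), and PP.
- **(b) Delete the cancellation rule and the assumed cost direction.** Always report incremental cost and incremental effect with 95% intervals. Give the ICER where it is interpretable; otherwise state which therapy, if any, is dominant.
- **(c) Minor.** State whether culture and susceptibility testing is charged to one arm or both. The choice is the sponsor's.

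The cost is SAP wording and slightly more analysis, with no new patients or visits. Cost is scheduled only at day 56, so naming all randomised patients does not recover the costs of those who miss that visit. That is why (a) needs a stated missing-cost method.

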6.1 Randomization and blinding

Eligible patients will be randomly allocated to receive either susceptibility-based tailored therapy (tailored therapy) or empirical bismuth quadruple therapy (empirical therapy) in a 3:1 ratio. An independent statistician at Shanghai Jiao Tong University College of Basic Medical Sciences generates the computerized random number sequence and used a permuted block randomization with a block size of eight. All investigators is masked to the randomization sequence. Allocation is concealed in an opaque envelope until the intervention was assigned. Envelopes will be kept at Renji Hospital. After the written informed consents would be obtained from eligible patients, the independent research assistant will open envelopes by randomization sequence and telephone study staff to give them each patient's treatment allocation. This study is an open-labeled trial and patients are not blinded. The technicians, who perform the H. pylori tests (rapid urease test, culture, antimicrobial susceptibility testing, and urea breath test) or fill in the questionnaires, will be blinded to treatment allocation.

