6.2 Intervention

(1) Empirical therapy

Esomeprazole 20 mg, bismuth potassium citrate 600 mg taken twice a day, amoxicillin 1 g, and metronidazole 500 mg taken three times a day for 14 days.

(2) Tailored therapy

Tailored therapy is based on antimicrobial susceptibility of clarithromycin, metronidazole and levofloxacin. a) If the H. pylori strain of one patient was sensitive to clarithromycin, clarithromycin triple therapy (EAC) will be given: esomeprazole 20 mg, amoxicillin 1 g, and clarithromycin 500 mg taken twice a day; b) If the strain was resistant to clarithromycin but sensitive to metronidazole, metronidazole triple therapy (EAM) will be given: esomeprazole 20 mg, amoxicillin 1 g, and metronidazole 500 mg taken twice a day. c) If the strain was resistant to both clarithromycin and metronidazole but sensitive to levofloxacin, levofloxacin triple therapy (EAL) will be given: esomeprazole 20 mg, amoxicillin 1 g taken twice a day, and levofloxacin 500 mg taken once a day. d) If the strain was resistant to all three antibiotics, bismuth quadruple therapy (EBA₂M₄) will be given: esomeprazole 20 mg, bismuth potassium citrate 600 mg, amoxicillin 1 g taken twice a day, and metronidazole 500 mg taken four times a day. Study treatment regimens will be all given 14 days.

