10.3 Statistical methods

Comparative superiority of the two groups was assessed through hypothesis testing (one-sided Z test) and derivation of a two-sided 95% confidence interval (CI) of difference based on H. pylori eradication rate. If p-value of the testing less than 0.025 and the lower bound of the 95% CI greater than zero, superiority of susceptibility-based therapy over empirical therapy could be concluded.

Between-group differences were evaluated using Student's t-test for continuous variables and Pearson's χ^2 /corrected χ^2 or Fisher's exact test for categorical variables, as appropriate. All p-values were two-sided except the testing of superiority, and were considered statistically significant if p-value less than 0.05.

Subgroup analyses of eradication efficacy were performed based on the results of antibiotic susceptibility test and compliance assessment.

11 Ethical principles

The study is registered in ClinicalTrials.gov. The study protocol is approved by the Ethics Committee at all institutions, and the study will be performed according to good clinical practice and the Declaration of Helsinki.

Before each patient is selected into the study, the physician of the study have the responsibility to tell patients or their designated agents the purpose, process, completion and comprehensively introduce possible adverse reactions, risks to bear, possible benefits and other information all-round and detailed, making the patients know their rights. We are ordered to inform the patients of having the right to decide whether to participate in the study, as well as the right to withdraw the study at any time without any discrimination. The patients or their legal representatives should sign the informed consent after carefully reading and fully understanding, and retain the signature page of the copy.

12 References

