Subjects without AEs

Subjects with AEs

Total

AE, adverse event.

Final Statistical Analysis Plan

This statistical analysis plan includes the details of study sample size calculation and statistical methods for analysis of outcomes and safety.

Table of Contents

1. Sample size estimation	68
2. Definition of populations for analysis	68
3. Evaluation of baseline characteristics	68
4. Evaluation of primary outcomes	70
5. Evaluation of secondary outcomes	70
6. Additional analyses	72
7. Table Design	73

1. Sample size estimation

Assuming 96.5% eradication rate of susceptibility-based therapy in our trial, 88.9% eradication rate of empirical therapy, a superiority margin of >0 , a power of 80%, an alpha of 0.05 (one-sided), a ratio of 3:1, at least 260 subjects in susceptibility-based therapy and 87 subjects in empirical therapy will be required to show superiority of susceptibility-based therapy over empirical therapy on the basis of H. pylori eradication rate. Taking into consideration of 10% lost to follow-up, at least 382 participants (286 for tailored therapy and 96 for empiric therapy) is expected to be recruited for the study.

2. Definition of populations for analysis

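### Cost is compared by Student t test under 3:1 allocation, although four regimens against one make unequal cost variances likely; Welch's test would be better calibrated

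*Combined protocol and SAP*

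**What the plan says.** Final SAP 5.3(1) defines a patient's medical cost as the total of visit, endoscopy, culture, susceptibility testing, eradication treatment and adverse-event treatment. The comparison between arms "will be performed in the PP analysis populations using Student t test". No confidence interval for the cost difference is specified.

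Final protocol 10.3 gives the same general rule: "Between-group differences were evaluated using Student's t-test for continuous variables". It also fixes the level: "All p-values were two-sided except the testing of superiority, and were considered statistically significant if p-value less than 0.05". The cost comparison is therefore two-sided at 0.05. Neither document provides for unequal variances.

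Final protocol 6.1 allocates patients to tailored therapy "or empirical bismuth quadruple therapy (empirical therapy) in a 3:1 ratio". Under final protocol 6.2 the empirical arm has one fixed regimen. The tailored arm has four, labelled a to d, chosen by resistance pattern; the last begins "If the strain was resistant to all three antibiotics, bismuth quadruple therapy".

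Cost-effectiveness is a secondary objective (final protocol 2.2(3)). The cost measures themselves are listed under other pre-specified outcomes (final protocol 9.3).

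**The concern.** Student's test estimates one common variance. With equal arms this hardly matters, because the pooled standard error equals the correct one even when the variances differ. With 3:1 allocation that protection is lost: the pooled variance is dominated by the larger arm, while the true standard error depends mostly on the smaller one.

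The design gives a reason to expect unequal variances. Prescribed drug cost is essentially constant in the empirical arm. In the tailored arm it varies unless the four regimens happen to cost the same, and they contain different drugs: only one includes bismuth and only one levofloxacin. The final protocol's background gives clarithromycin resistance of 21-52%. By subtraction, 48-79% of tailored patients would receive regimen a and the rest regimens b to d, so the mix is real.

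At stake is the calibration of the cost p-value and of any interval later derived from the same standard error. The SAP already expects tailored therapy to cost more, so the informative result is the size of the difference and its precision.

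**Working it through.** **Arm sizes.** The documents give no calculation for cost, so the arm sizes come from the primary sample size in final SAP section 1. Its inputs are "Assuming 96.5% eradication rate of susceptibility-based therapy in our trial", "88.9% eradication rate of empirical therapy" and "a power of 80%, an alpha of 0.05 (one-sided), a ratio of 3:1". With pE = 0.889, pT = 0.965 and weighted mean p = (0.889 + 3 × 0.965)/4 = 0.946:

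nE = [1.645 × √(0.946 × 0.054 × 4/3) + 0.842 × √(0.889 × 0.111 + 0.965 × 0.035/3)]² / 0.076² ≈ 86.9

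This rounds up to 87 empirical, and 3 × 87 = 261 tailored, against the stated 87 and 260. The plan's figure is reproduced. Recruitment of 286 and 96 is 260 × 1.10 and 87 × 1.10, rounded. I use 260 and 87 as a stand-in for the per-protocol population.

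**Standard errors.** Let r be the ratio of the cost SDs, tailored to empirical, with the empirical SD set to 1. The values of r are assumptions.

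- Pooled variance: sp² = (259 r² + 86)/345
- Student SE: √[sp² × (1/260 + 1/87)]
- True SE: √(r²/260 + 1/87)

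Example, r = 2: sp² = (259 × 4 + 86)/345 = 3.252. Student SE = √(3.252 × 0.01534) = 0.2234. True SE = √(0.01538 + 0.01149) = 0.1639. Ratio = 1.36.

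Example, r = 0.5: sp² = (64.75 + 86)/345 = 0.437. Student SE = √(0.437 × 0.01534) = 0.0819. True SE = √(0.00096 + 0.01149) = 0.1116. Ratio = 0.73.

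**Size.** The true size of each two-sided 5% test was simulated with 40,000 replicates of normal data at 260 and 87.

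| SD ratio, tailored/empirical (assumed) | Student SE / true SE | Size, Student | Size, Welch |
|---|---|---|---|
| 0.5 | 0.73 | 0.151 | 0.050 |
| 0.67 | 0.82 | 0.104 | 0.050 |
| 0.8 | 0.90 | 0.079 | 0.049 |
| 1 | 1.00 | 0.048 | 0.049 |
| 1.25 | 1.12 | 0.027 | 0.047 |
| 1.5 | 1.22 | 0.017 | 0.050 |
| 2 | 1.36 | 0.009 | 0.050 |
| 3 | 1.53 | 0.003 | 0.049 |

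Results at 286 and 96 are nearly the same.

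**Why more patients do not help.** In large samples at 3:1 the squared SE ratio tends to (3r² + 1)/(r² + 3), which does not contain n. At r = 2 it is 13/7, with square root 1.36. At r = 0.5 it is 1.75/3.25, with square root 0.73. At 1:1 the corresponding ratio is 1 for every r.

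**The case against.** The strongest reply is that nothing in the documents shows the variances to differ. They give no cost mean, SD or price. Four regimens make only the drug component vary. Culture and susceptibility testing at a uniform charge shifts the mean and leaves the variance alone. Adverse-event costs could make either arm the more variable. If the SDs are close, Student's test is correct (0.048 above). All of this stands: unequal variance is a reasonable expectation from the design, not a stated fact.

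A reader might infer that the planned test produces false positive cost findings. The documents do not support that. The only mechanism they offer, the regimen mix, makes the larger arm more variable and the test conservative. Inflation needs the smaller, empirical arm to vary more, for example through adverse-event costs, and the documents give no sign of this.

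A reader might also infer that the ICER or a planned interval is wrong. The cost ratio and the ICER use mean costs, and the difference in means is the same under Student and Welch. No interval is planned for the cost difference or for the ICER, so none in the plan can be wrong.

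Finally, the cost p-value decides nothing. Whether an ICER is calculated depends on the eradication rates, and the SAP presumes the sign of the cost difference. That limits the importance of the point. It does not make the pooled test the better choice.

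**Conclusion.** The point holds as a minor one. Under 3:1 allocation the planned test relies on equal cost variances, which the regimen structure makes doubtful. In the likelier direction, SD ratios of 1.5 to 2 make the standard error about 22-36% too wide and the size about 1-2%; precision is understated and power is lost. In the opposite direction, ratios of 1:1.5 to 1:2 make it about 18-27% too narrow, with a size of about 10% at 0.67 and 15% at 0.5.

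These figures rest on assumed SD ratios, normal data, the usual pooled reading of Student's test, and arms of about 260 and 87. Only the cost p-value and any interval built from the same standard error are affected. It would go too far to call the test wrong or the variances unequal by design.

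**What to change.** In final SAP 5.3(1), replace the Student t test with the difference in mean cost (tailored minus empirical) and its 95% confidence interval from Welch's unequal-variance t test. Note the exception in final protocol 10.3 so that the two documents agree. This changes one phrase in the SAP and one option in the code, and needs no new data. Welch held 0.047 to 0.050 at every SD ratio in the table, including equal SDs.

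A non-parametric bootstrap stratified by arm is an optional alternative if costs are markedly skewed. It could also give joint uncertainty for incremental cost and eradication, but that would be a new analysis with more work than the one-phrase change.

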Now culture-based susceptibility testing for *H. pylori* is rarely performed in standard practice. This may be due to several major limitations: they are time-consuming, costly, and invasive procedures, culture difficulty, and et al. So empirical therapy would be needed for most patients over the world. In the settings with high antibiotic resistance, only bismuth quadruple therapy (BQT) is the recommended first-line treatment, and any non-BQT therapy (triple, concomitant, hybrid, or sequential) would not be more effective option.(1) Our previous study showed that substitution of amoxicillin for tetracycline in a 14-day BQT containing 1,600mg/d of metronidazole eradicated 96.4%(54/56) of metronidazole susceptible strains and 93.3%(42/45) of metronidazole resistant strains when used as first-line *H. pylori* therapy.(10). Fewer studies had

compared the effect of susceptibility-based therapy versus BQT for first-line *H. pylori* eradication, except one.(11)

In this study, we will evaluate the efficacy, safety and compliance of pretreatment culture and susceptibility-based tailored therapy to treat naïve patients with *H. pylori* infection. Susceptibility-based therapy will use [name] DY et al's recommendation, in which proton pump inhibitors, amoxicillin, and third susceptible drug triple therapies will be given after testing the susceptibility to clarithromycin, metronidazole and levofloxacin, or bismuth quadruple therapy was given if no susceptible antibiotics.(12) The comparator is novel bismuth quadruple therapy in which tetracycline was replaced by amoxicillin, without reference to antimicrobial susceptibility.

2. Objective

[figure not shown]

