2.2 The secondary objective

- (1) To compare the safety and compliance of tailored therapy with empiric modified bismuth quadruple therapy;
- (2) To evaluate the impact of antibiotic resistance on eradication rates;
- (3) To evaluate the cost-effectiveness of susceptibility-based tailored therapy in treating naïve patients with *H. pylori* infection.

3. Follow Diagram

4. Study Design

This study is a prospective, superiority-designed, multi-center, open-label, randomized controlled trial conducted in five hospitals in Shanghai, China including Renji Hospital, Ruijin Hospital, Zhongshan Hospital, Shanghai general Hospital, and Shanghai Tenth People's Hospital.

5. Study population

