5.1 Inclusion criteria

- (1) Participants with non-ulcer functional dyspepsia or scarred peptic ulcer disease;
- (2) Ability and willingness to participate in the study and to sign and give informed consent;
- (3) confirmed H. pylori infection with positive results on both rapid urease testing and culture

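### The planned cost-effectiveness ratio applies only to patients whose culture grew, while the objective covers all treatment-naïve infected patients

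*Combined protocol and SAP*

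**What the plan says.** Final Protocol 2.2(3) sets this secondary objective: "To evaluate the cost-effectiveness of susceptibility-based tailored therapy in treating naïve patients with *H. pylori* infection". Entry under 5.1(3) requires "confirmed H. pylori infection with positive results on both rapid urease testing and culture". The schedule puts biopsy, urease test, culture and susceptibility testing at visit 1 (day −14) and allocation at visit 2 (day 0). Section 6.1 randomises only those who qualify: "Eligible patients will be randomly allocated to receive either susceptibility-based tailored therapy (tailored therapy) or empirical bismuth quadruple therapy".

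Final SAP 5.3(1) defines the cost: "Medical cost of one patient is overall cost including visit, endoscopy, H. pylori culture, susceptibility testing, eradication treatment, and adverse event treatment". It adds: "Comparisons of medical cost between the tailored therapy and empiric therapy will be performed in the PP analysis populations using Student t test". Section 5.3(3) divides the cost difference by the eradication difference, in RMB per percentage point, and does so only if tailored therapy eradicates more. It names no analysis population for the eradication difference. It takes for granted that tailored therapy is dearer: "Obviously, the tailored therapy will cost more because of additional bacterial culture and antibiotic susceptibility testing".

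The Final Protocol's Background explains why culture-based testing is rarely used: "they are time-consuming, costly, and invasive procedures, culture difficulty, and et al". No readable section gives a culture success rate, costs a culture that failed before randomisation, or plans a sensitivity analysis on culture yield.

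**The concern.** A clinic that adopts culture-guided therapy pays for a culture in every infected patient it tests. Where the culture fails, it has paid and has no susceptibility result to act on. The trial removes those patients before allocation, so its cost and its eradication gain both describe the strategy after a successful culture. The protocol itself counts culture difficulty among the strategy's main limits, so this is a foreseeable part of its cost-effectiveness.

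Read against the objective, the planned ICER assumes that every culture succeeds. Moving the cost comparison from per-protocol to intention-to-treat would not help, because the selection happens at entry.

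**Working it through.** **The plan's own figures.** The documents give no ICER, unit cost or culture success rate, so there is no ICER to reproduce. Two planning figures from Final SAP section 1 are used here:
- The eradication gain: D = 96.5 − 88.9 = 7.6 points.
- The recruitment target of 382, from 260 × 1.1 = 286 and 87 × 1.1 = 95.7, rounded to 96. The evaluable numbers reproduce: a pooled two-proportion formula at one-sided 0.05, 80% power and 3:1 gives 87 and 261, against the stated 87 and 260.

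**Symbols**
- c: cost of one culture.
- a: net extra cost once an isolate exists (susceptibility testing plus the regimen cost difference).
- s: culture success among infected, otherwise eligible patients. It is not in the documents; 60% to 90% is assumed.

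**Formulas, with culture charged to the tailored arm**
- Plan: (c + a)/D.
- Culture-first strategy, per infected patient cultured, with failed cultures given the empirical arm's cost and eradication rate (assumption): extra cost c + s·a, gain s·D, so ICER = (c + s·a)/(s·D) = c/(sD) + a/D.
- Shortfall of the plan: c(1/s − 1)/D. It is positive for every s below 1 and does not depend on a.
- Ratio of the two ICERs: (c/s + a)/(c + a).

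**Results with D = 7.6** (the relation of a to c is assumed)

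| s | Culture component × 1/s | Gain per patient cultured, 7.6s | Shortfall per point, in units of c | Whole ICER, a = c/2 | Whole ICER, a = c | Whole ICER, a = 2c |
|---|---|---|---|---|---|---|
| 90% | 1.11 | 6.84 | 0.015 | +7% | +6% | +4% |
| 80% | 1.25 | 6.08 | 0.033 | +17% | +13% | +8% |
| 70% | 1.43 | 5.32 | 0.056 | +29% | +21% | +14% |
| 60% | 1.67 | 4.56 | 0.088 | +44% | +33% | +22% |

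**Where the increase comes from.** Take a = c and s = 80%. The extra cost per patient cultured is c + 0.8c = 1.8c, below the plan's 2c. The gain falls from 7.6 to 6.08 points. The ICER goes from 2c/7.6 = 0.263c to 1.8c/6.08 = 0.296c, a ratio of 1.125. The rise comes from dilution of the gain.

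**Uncosted cultures.** Randomising 382 culture-positive patients takes 382/s cultures: about 424, 478, 546 and 637 at s = 90%, 80%, 70% and 60%. About 42, 96, 164 and 255 failed cultures would then be left out.

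**If culture is charged to both arms.** Every patient is cultured at visit 1, and 5.3(1) does not say which arm bears the cost. If both do, c cancels and the planned ICER becomes a/D. The shortfall is then c/(sD), larger than before by c/D. At s = 80% that is 1.25c/7.6 = 0.164c per point instead of 0.033c.

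**The case against.** The strongest reply is that this is a matter of scope. A within-trial ICER in randomised patients is a legitimate quantity, and the same entry rule limits the primary eradication comparison. That stands, and it is why the remedy is a label and a sensitivity analysis. It does not remove the mismatch, because the objective is not restricted to culture-positive patients.

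Other replies also limit the point:
- A reader might infer that the whole testing cost should be scaled by 1/s. The documents do not support that. SAP 5.3(1) lists culture and susceptibility testing as separate items, and Final Protocol section 7 measures MICs on grown bacteria, so a failed culture incurs no susceptibility-testing cost.
- A reader might infer that the plan understates testing cost per patient tested. It does not: with failures included, that cost is c plus s times the susceptibility-testing cost, which is no higher than the plan's.
- A reader might infer that the percentages hold whichever arm bears the testing cost. Only the direction does.
- The fallback for failed cultures is an assumption. Final Protocol 6.2(2) has only branches that follow a susceptibility result, and another route, such as a repeat culture, would give a different ICER.
- Some urease-positive, culture-negative patients may be uninfected. Counting them as failures makes s too low and the correction too large.
- The flow diagram (Final Protocol section 3) is not visible in the text reviewed, so it may already carry the screening count.

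**Conclusion.** The point holds as a minor one. The ICER in Final SAP 5.3(3) is conditional on successful culture, and the objective is wider. If failed cultures take the empirical arm's cost and eradication rate, and culture is charged to the tailored arm, the planned figure is too low by c(1/s − 1)/D for any s below 1, in favour of tailored therapy. Only the culture component rises: by 11%, 25%, 43% and 67% at assumed s of 90%, 80%, 70% and 60%. The whole ICER rises by about 6%, 13%, 21% and 33% if c equals a. The actual size cannot be computed from the documents, because s, c and a are not given.

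A reader might infer that a finding in favour of culture-guided therapy would be overturned. The documents do not support that: they give no unit costs, no willingness-to-pay threshold and no rule for judging a therapy that is both dearer and better. Nor does the point affect the primary efficacy analysis.

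**What to change.** In Final SAP 5.3:
1. State that culture and susceptibility testing are charged to the tailored arm only, as the sentence in 5.3(3) implies.
2. Label the planned ICER *conditional on successful culture*.
3. Beside it, report c/(sD) + a/D as a sensitivity analysis.
4. Estimate s at visit 1: otherwise eligible, urease-positive patients with a successful culture, divided by all such patients who were cultured. Report both counts. Vary s over a range, because some urease results may be false positives.
5. State that giving failed cultures the empirical arm's cost and eradication rate is a costing assumption, not a treatment rule.

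The cost is one count from visit 1, where urease testing and culture already take place, and one extra line of analysis. No patients or procedures are added. The downside is a second ICER that is less favourable to tailored therapy and rests on a stated assumption about failed cultures.
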